6.2.6 Chart audits

We will replicate procedures described in previous publications to measure rates of actions such as completion of cognitive assessments, orders for neuroimaging, referrals for neurocognitive testing, specialists, and orders for medications in the accrued population.^[25] We will also audit the charts of 50-100 patients each in the CI-CDS and UC treatment groups, until saturation is reached. Chart audits are an important supplement to the EHR-based data to the extent that some clinician actions are difficult to obtain from fixed data fields in the EHR, including the presence and quality of care plans, caregiver identification, release of information authorization completion, and individualized recommendations for managing potentially distressful symptoms and safety issues.

6.2.7 Patient / caregiver dyad interviews

We will conduct semi-structured interviews with patient/caregiver dyads from randomized study clinics who are at elevated risk, recently screened, or newly diagnosed with CI to explore their experiences with screening, assessment, or diagnosis as well as their perceived preparedness for subsequent disease management. We will recruit study-accrued patients with recent study-eligible primary care index encounters to participate in the interviews. Following best-practice in qualitative data collection methods,^[82] approximately twenty dyads will be recruited to participate. Interview guides will be designed in close partnership with qualitative and clinical experts to elicit rich qualitative patient and caregiver perspectives. A semi-structured design approach will be used consisting of 4-7 open-ended root questions each followed by a set of open-ended probes. Interviewers are trained and experienced in qualitative data collection within the health system setting. Interviewers will receive additional study-specific training related to CI care and the CI-CDS intervention. Practice interviews and on-going supervision will be conducted to ensure consistent, valuable data are collected. Detailed field notes will be collected using REDCap and, with permission, interviews will be recorded and transcribed. A thematic content analysis will be designed using combined inductive and deductive approaches to explore the perceived impact of clinic experience on addressed/unaddressed concerns, and resulting benefit/distress from screening, feelings about preparedness for future decisions, support, and distress. Learnings will be used to understand patient experience and inform future implementation and to design extensions of the CI-CDS related to disease management.

7. SAFETY ASSESSMENTS

7.1 Specification of Safety Parameters

This pragmatic trial introduces the CI-CDS system as an intervention delivery tool to clinics randomized to an intervention treatment group, where it provides data-informed clinical decision support to clinicians as an adjunct to the usual care they provide at primary care visits. The CI-CDS system is designed to facilitate the provision of accepted standards of care.

With this work, we are not attempting to change the standard of care for managing patients with CI in primary care, but rather are attempting to help clinicians achieve this standard of care in CI management such as through screening patients for CI or recognizing CI in the EHR. Primary care clinicians will be trained that, as with other clinical decision tools, the CI-CDS system is meant to supplement but not supersede clinical judgment. Clinicians will be able to choose to follow or to not follow the guidance of the CDS at any given time for any given patient.

Clinicians will be asked to use the Feedback Tab within the tool to let the study team know of questions or potential errors in the CDS. Additionally, clinicians will be trained to let the research team know via the Feedback Tab when their clinical judgment is inconsistent with the CDS. This feedback will be monitored by the treatment team and the CDS algorithms adjusted if indicated.

Actions suggested by the CI-CDS system are consistent with standard care for patients who meet intervention eligibility criteria, and therefore are unlikely to pose specific risks to their safety beyond those inherent to primary care. As such, we will not be monitoring safety events specific to the CI-CDS intervention or the content it delivers. Similarly, the intervention does not involve laboratory measures beyond those assessed in usual primary care, and as such we do not specify laboratory safety parameters. We will monitor emergency department visits, hospitalizations, suicide attempts, and deaths as safety events among all accrued patients from prior to their index visit through the end of the observation period although these events are unlikely to be related to the intervention.

7.2 Methods and Timing for Assessing, Recording, and Analyzing Safety Parameters

We propose to use passive surveillance of EHR and administrative data sources to monitor the occurrence of safety events. Benefits to this approach are that safety events can be ascertained identically for all accrued patients in all randomized clinics. Documentation will occur in the course of delivering health care or administering health insurance so that records should be reasonably accurate and complete with minimal and randomly missing information. When care for safety events is delivered outside the HealthPartners care system, health care claims can document their occurrence for patients who are also health plan members. Missing information due to events for which patients do not seek care or care that escapes documentation in the EHR or claims will be assumed to occur equally across treatment groups.

7.3 Clinician Feedback and Safety Events

7.3.1 Clinician Feedback

This intervention is being delivered by way of CDS prompts to influence clinician actions to incorporate evidence-based best practice standards related to CI. Prior to implementation, we will train all intervention clinicians and their rooming staff on the importance of helping us identify any clinician-identified safety events or near-misses that may be related to the EHR or CI-CDS. We will systematically educate them in identification of potential safety events and near-misses and informing us of these events via use of the Feedback Tab in the CDS or email. We will also ask clinicians to notify us of any clinical situations where their clinical judgment differs from the CI-CDS.

Use of the Feedback Tab will automatically generate an email that is sent to study team members, including investigators and programmers. The study team will then discuss this

feedback and any necessary actions, and reply to the clinician to answer the question, discuss steps taken to address the issue, or gather additional information if needed to further troubleshoot. Clinicians will be asked to submit feedback any time their clinical judgment is inconsistent with the CDS tool. Additionally, the emails of study investigators will be listed in the training materials for clinicians, and clinicians will be encouraged to contact the study team directly with any questions or concerns if they would rather not use the Feedback Tab in the CI-CDS. This feedback will be provided to the DSMB at a frequency determined by the DSMB.

7.3.2 Safety events

Adverse Event (AE):

As this is a minimal risk study, with the CI-CDS intervention layered on top of usual care, adverse events will not be collected in the context of this trial.

Safety Events:

- emergency department visits
- hospitalizations
- suicide attempts
- death

We will extract data from the EHR and administrative databases to monitor safety events that occurred from 1 year prior to each accrued patient's index visit date through the end of the observation period. The following activities will be carried out at a frequency determined by the DSMB. The study statistician will assemble the random, unique study identifier and index visit date for all accrued patients. A study programmer will extract data elements needed to characterize the patient sample and to quantify rates of emergency department visits, hospitalizations, suicide attempts, and deaths. State preliminary manner of death data are sent to HealthPartners monthly, with a lag of about a month; these data and final adjudicated cause of death data are incorporated into HealthPartners databases upon receipt. The statistician will assemble a safety report and provide it to the co-PIs, OCHIN Lead Co-Investigator and the DSMB.

The DSMB report will provide information regarding patient accrual, intervention delivery and safety events. Patient accrual will be tracked through monthly and cumulative counts of actual and expected counts of index visits. Pre-randomization clinic characteristics and index visit date patient characteristics will be provided overall and by treatment group within site. CI-CDS use will be tracked monthly and cumulatively by treatment arm within site to monitor intervention adherence (intervention clinics) and check for contamination (control clinics).

The following metrics will be calculated for each safety event: total number of events (allowing multiple per patient), proportion of accrued patients with at least one event, and the event rate in patient-years. Each metric for each event will be compared between the treatment groups (intervention vs. control) and over time (post-index vs. 1 year pre-index). Data from the year prior to each patient's index visit will provide baseline data regarding the prevalence of each safety event. Post-index data will be compared to baseline data by treatment group to identify differential changes in safety event rates.

As safety events will be summarized by treatment arm using EHR and administrative data, it is not feasible to assess relationship to the study intervention, *per se*. Instead, the study team and DSMB will evaluate safety data at an interval determined by the DSMB to evaluate differences in safety event rates across treatment groups.

7.3.3 Follow-up for Safety Events

As safety events will be assessed retrospectively via EHR and administrative data and given that the study team does not interact directly with patients (but instead they are treated by their primary care clinicians), the study team will not be providing follow-up for safety events. Instead, we can presume that the primary care clinicians and other medical professionals who are providing the patients' clinical care will manage these events.

7.4 Safety Monitoring

This study will be monitored by an NIA-appointed Data and Safety Monitoring Board (DSMB). Tables will summarize, within site and by blinded treatment group, (a) metrics pertaining to patient accrual; (b) performance of the CI-CDS system; (c) pre-randomization clinic characteristics and index visit patient characteristics; and (d) safety measures. Reports will be provided to the DSMB at a frequency the DSMB requests. The DSMB will provide an opinion on whether there is support for continuation of the trial, evidence that study procedures should be changed, or evidence that the trial should be halted for any reason, such as the safety of study participants, the efficacy of the treatment under study or inadequate trial performance.

8 INTERVENTION DISCONTINUATION

Once randomized, all primary care clinics are anticipated to remain enrolled for the duration of the study. All accrued patients will be followed for the duration of the observation period (i.e., end of study) unless they die or leave the care system. Patients who have opted out of research will be excluded from all analyses.

9 STATISTICAL CONSIDERATIONS

9.1 General Design Issues

The specific aims of the R33 phase of this trial are: To evaluate the effect of the CI-CDS system on rates of CI detection, clinician confidence, and healthcare utilization costs in a pragmatic cluster-randomized trial of at least 30 primary care clinics randomized to CI-CDS or UC.

H1: Patients with elevated CI risk at index visits in CI-CDS compared to UC clinics will have significantly higher rates of CI detection as indicated by EHR documentation of CI diagnosis in up to 24 months of follow up.

H2: Clinicians at CI-CDS compared to UC clinics will have significantly more confidence in diagnosing and managing CI, as assessed through clinician surveys.

H3: Among a subset of insured patients with elevated CI risk at index visits, those at CI-CDS clinics will have significantly lower healthcare utilization costs related to emergency room and inpatient visits in the follow-up period compared to similar patients at UC clinics.

The primary effectiveness study is a pragmatic clinic-randomized trial that will assess the effectiveness of the CI-CDS system to impact outcomes that are important to patients, clinicians, and health system. This trial will be followed by a replication study in up to 30 randomized clinics in a separate health care system (replication site). The minimal eligibility criteria at the clinic and patient level help ensure that the results of these assessments will be generalizable to a range of clinical settings and patients. The intervention, the CI-CDS system, will be operating in live, primary care settings. At the end of the replication site intervention period, the study team will work with replication site leadership to transition the CI-CDS system from an experimental technology to the system-wide standard of care if so desired by leadership. The transition is readily accomplished by enabling user interface functionality in clinics that had been randomized to the UC group and by adding new clinic locations to the CI-CDS algorithms.

9.2 Sample Size and Randomization

9.2.1 Treatment Assignment Procedures

Clinics will be randomized 1:1 to CI-CDS or UC using simple randomization. Randomizing by clinic rather than clinician or patient is the most effective way to minimize risk of intervention contamination. Patients tend to receive most of their care over time at a single clinic, and clinicians tend to practice at a single clinic, so it is reasonable to assert that the risk of intervention contamination across clinics is low. However, it is common for patients to see more than one clinician in a clinic location over time. Randomizing by clinician is not preferable because it would increase the number of patients with multiple visits during the intervention period who would be exposed to both treatment groups over the course of these visits. Repeated use of the CI-CDS system may alter practice patterns so that clinicians may diagnose and manage care for patients with CI in the absence of prompts provided by the CDS. Randomizing by patients is not preferable because it would result in care for UC patients that was contaminated by changes in clinician practice patterns.

Each patient will be assigned to the clinic in which his or her index visit takes place, and as such will be assigned to the treatment group to which their clinic was randomly assigned. Post-index visits may take place in the same or different clinics or treatment groups relative to the index visit and may or may not be eligible for the CI-CDS to offer treatment recommendations. In keeping with an intent-to-treat principle, all index and post-index visits and outcome measures for each patient will be attributed to the treatment group assignment of the clinic where the index visit took place.

The nature of the intervention prevents study personnel, clinic leaders or primary care clinicians from being blinded to the treatment group assignment of each clinic.

9.2.2 Sample Size Justification

The primary hypothesis test will compare patients in CI-CDS clinics to patients in UC clinics on the likelihood that CI is diagnosed during the observation period. We conducted a power analysis to estimate the minimum detectable rate of new CI diagnoses given ranges of assumptions about analytic sample sizes, proportions of patients currently meeting outcome criteria, and clinic intraclass correlation (ICC_{clin}). We used data accrued into the CI-CDS

system during the silent pilot phase from the R61 to identify patients who met intervention eligibility criteria at clinic visits (sections 4.1, 4.2). Based on the pilot CI-CDS data, we estimate that, on average, about n=100 patients in each of at least 30 clinics will likely have an index visit in over the course of a 12-month accrual period.

An EHR-based cohort that consisted of patients who were age ≥ 65 and had a primary care visit between September 2021 and August 2022 was assembled to provide estimates of CI diagnosis rates in primary care clinics that were candidates for randomization. The proportion of patients who had at least one CI diagnosis code at an encounter or listed on their active problem list during the 12-month period was 2.3% among all patients in the cohort, and 15.1% among those who had a MiniCog<3 during the period. There was substantial variation in CI recognition among all patients, $ICC_{clin}=0.03$, and among those with MiniCog<3, $ICC_{clin}=0.04$.

Based on these data-informed estimates, we used the following assumptions regarding the primary effectiveness study for the power analysis: 30, 34 or 38 clinics randomly assigned 1:1 to CI-CDS or UC, n=100 patients per clinic, $ICC_{clin}=(0.03, 0.04, 0.05)$ and diagnosis rates = (8%, 12%, 16%) in UC clinics. The correlated sample size estimate, N, was divided by the design effect (deff; $1+(n-1)*ICC$) to estimate an equivalent independent patient sample size (i.e., $N_{eff}=N/deff$). The power analysis (power=0.80, $\alpha_2=0.05$) estimated the minimum detectable CI-CDS CI diagnosis rate from a single binary predictor in a logistic regression model using the downwardly adjusted independent sample size estimate.[84]

Given the median assumptions for number of randomized clinics, ICC_{clin} and CI diagnosis rate, the study is powered to detect a diagnosis rate of 19.8% in CI-CDS clinics relative to 12% in UC clinics (Table 1). The absolute increase in diagnosis rates ranges from 5.6% (38 clinics, $ICC_{clin}=0.03, 8\%$) to 10.2% (30 clinics, $ICC_{clin}=0.05, 16\%$) across the range of these assumptions.

A comparable power analysis was conducted for the replication site analysis of CI diagnosis rates among patients in CI-CDS relative to UC clinics. Assumptions about the number of randomized clinics (22, 26, 30), patients per clinic (n=60) and CI diagnosis rate (4%, 8%, 12%) were changed to acknowledge the likely smaller sample size and shorter observation period relative to the primary effectiveness site. Given the median assumptions for number of randomized clinics, ICC_{clin} and CI diagnosis rate, the study is powered to detect a diagnosis rate of 16.5% in CI-CDS clinics relative to 8% in UC clinics (Table 2). The absolute increase in diagnosis rates ranges from 5.5% (30 clinics, $ICC_{clin}=0.03, 4\%$) to 9.7% (22 clinics, $ICC_{clin}=0.05, 12\%$) across the range of these assumptions.

Table 1. Minimum detectable rates of CI diagnosis in CI-CDS clinics assuming n=100 accrued patients per clinic, 30-38 clinics, $ICC_{clin} = 0.03-0.05$ and UC diagnosis rates = 8-16%.

clinics	ICC_{clin}	UC diagnoses (%)		
		8%	12%	16%
30	0.03	14.4	19.4	24.2
	0.04	15.3	20.4	25.2
	0.05	16.1	21.3	26.2
34	0.03	14.0	18.9	23.6
	0.04	14.8	19.8	24.6
	0.05	15.5	20.6	25.5
38	0.03	13.6	18.5	23.2
	0.04	14.4	19.4	24.1
	0.05	15.1	20.1	24.9

Table 2. Minimum detectable rates of CI diagnosis in replication site CI-CDS clinics assuming n=60 accrued patients per clinic, 22-30 clinics, $ICC_{clin} = 0.03-0.05$ and UC diagnosis rates = 4-12%.

clinics	ICC_{clin}	UC diagnoses (%)		
		4%	8%	12%
22	0.03	10.7	16.4	21.6
	0.04	11.6	17.4	22.7
	0.05	12.4	18.3	23.7
26	0.03	10.0	15.6	20.7
	0.04	10.8	16.5	21.7
	0.05	11.5	17.4	22.6
30	0.03	9.5	15.0	20.1
	0.04	10.2	15.8	21.0
	0.05	10.9	16.6	21.8

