Replication: In addition to the primary effectiveness trial, the CI-CDS system will be implemented and evaluated at OCHIN, a network of safety net health centers clinics across the country. organized under a 501(c)(3) designation. Across the country, OCHIN's highly customized, centrally hosted EpicCare ambulatory system EHR is used in a broad network of primary care safety net settings including Federally Qualified Health Centers (FQHCs) and FQHC lookalikes, rural health centers (RHCs), school-based health centers, and county health departments. The replication site study design will be similar in that service areas with constituent primary care clinics will be randomized equally to a CI-CDS or UC treatment group. The CI-CDS system will be fully implemented in CI-CDS clinics and silently implemented in UC clinics (i.e., working in the background to collect data but not visible to clinicians). Patients will accrue into the study at index visits over a 6-month accrual period, with an approximately 6-month observation period for the last accrued patient, resulting in an ~12-month intervention period. See replication site-specific protocol details in **Section 15.5**.

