9.5 Data Analyses

9.5.1 Primary analysis

The H1 sample will consist of primary effectiveness site patients accrued from the CI-CDS and UC clinics who are at elevated risk for CI but without a CI diagnosis at index. The primary outcome is defined as at least one CI diagnostic code or CI diagnosis entry on the problem list at any time between the index visit and the end of the observation period (at least 12 and up to 24 months post-index), inclusive. H1 will be tested using a generalized linear mixed model (LMM) to account for clustering within randomized clinics and normalize the binary outcome via a distribution-appropriate link function (e.g., logit, log). Clinic-randomized treatment group and any patient covariates (e.g., age at index visit, sex, MC-PLUS risk score at index visit) will be treated as fixed effects.

Descriptive statistics will be calculated on all pre-intervention patient variables across all accrued patients, by treatment group and by clinic to ensure that key patient characteristics related to the risk of CI or its diagnosis (i.e., age, sex, comorbidities) are balanced across treatment arms. Imbalanced patient characteristics will be considered for inclusion as covariates in the primary analyses.

For H1, we will fit a generalized LMM in which the binary post-index CI diagnosis outcome will be predicted via a link function from fixed effects for the clinic-randomized predictor, γ_{10} , and patient covariates, γ_{0*} , and a random clinic intercept, v_j , such as:

$$\text{logit}(\text{diagnosis}_{ji}) = \gamma_{00} + \gamma_{10}\text{CI-CDS}_j + \gamma_{0*}(\text{pt covars})_{ji} + [v_j].$$

Parameter γ_{10} is expected to be positive and statistically significant, indicating that accrued patients in clinics randomly assigned to CI-CDS are more likely to receive a CI diagnosis in the observation period than patients in UC clinics, accounting for fixed effects and random clinic variation.

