4. SELECTION AND ENROLLMENT OF PARTICIPANTS

Primary care clinics

The OCHIN Lead Co-Investigator will collaborate with the HealthPartners Co-PIs to identify eligible service areas (groups of related clinics) that will be randomized 1:1 to the CI-CDS or UC treatment group. OCHIN will enroll at least three service areas with at least 10 total constituent primary care clinics as CI-CDS replication sites; a similar number of service areas and primary care clinics will serve as usual care (UC) replication sites. Stratified randomization by SA size may be used to balance the number of constituent clinics in each treatment group. Replication site clinics must currently have access to cardiovascular (CV) Wizard to be eligible for randomization. Service areas were chosen as a unit of randomization to avoid intervention contamination within groups of these highly related clinics.

CI-CDS and UC service areas will be approached for participation in the study. Service areas, and their constituent clinics, that agree to participate by allowing full or silent implementation of the CI-CDS system will be considered enrolled.

Recruitment will be conducted by the OCHIN study team, with support as needed from the HealthPartners staff. Eligible service areas and their clinics will be sent an introductory recruitment email with relevant study-related information, such as outlining the goals of the study, the CI Wizard tool, and an invitation to participate. Study team staff will follow-up via email, telephone, or video conference platform to answer any questions, provide demos of CI Wizard CDS, and/or share additional information regarding participation with service areas that are interested, as appropriate.

Once a service area agrees to participate, OCHIN will follow up with a Memorandum of Understanding (MOU) that outlines participation expectations, a timeline for study activities, and details regarding compensation. These MOUs will be signed by OCHIN and leadership at the participating service areas prior to starting study activities. Service areas will receive an impact payment of up to \$3000 as compensation for the time spent engaging in study activities. This impact payment will be distributed by OCHIN and is provided to the service area and not to any individual within the service area or clinic.

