9. STATISTICAL CONSIDERATIONS

9.2 Sample Size and Randomization

Operational considerations at the replication site make clinic-randomization impractical. To accommodate these considerations, randomization will be conducted by service area rather than clinic. Service areas eligible for randomization are those that currently have access to CV Wizard.

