9.2.1 Treatment Assignment Procedures

All eligible service areas will be randomized 1:1 to CI-CDS intervention or Control to maximize the likelihood that CI-CDS and UC service areas are similar on observed and unobserved characteristics. Service areas may be stratified based on number of clinics to ensure a balanced number of clinics between intervention and control groups. Service areas in the intervention group will be approached to participate in the study, which includes turning on the CI-CDS user interface. If they do not agree, they will be invited to turn on the CI-CDS invisibly to collect data in the background. CI-CDS service areas that agree to either of these options will be considered enrolled. Service areas randomized to UC that agree to run the CI-CDS invisibly in the background will be considered enrolled.

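### Replication power (16.5% vs 8%) assumes 22 to 30 randomised clinics, but OCHIN randomises service areas and no power is given for that design; the stated 9.7% upper bound should be 11.7%

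*Protocol*

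**What the plan says.** Protocol 9.2.2 carries the primary-site power method over to the replication site: "Assumptions about the number of randomized clinics (22, 26, 30), patients per clinic (n=60) and CI diagnosis rate" were changed, giving 16.5% against 8% at the median assumptions (26 clinics, ICC 0.04) with 80% power. Clustering is handled by a clinic-level design effect only. The text then says the detectable increase runs from 5.5% "to 9.7% (22 clinics", ICC 0.05, usual care 12%).

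Other parts of the Protocol describe a different unit:

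- Section 2, Replication paragraph: "service areas with constituent primary care clinics will be randomized equally to a CI-CDS or UC treatment group".
- Section 15.5, part 4: "OCHIN will enroll at least three service areas with at least 10 total constituent primary care clinics as CI-CDS replication sites", with a similar number of areas and clinics in usual care.
- Section 15.5, part 9.2: "randomization will be conducted by service area rather than clinic".
- Section 15.5, part 9.2.1: "All eligible service areas will be randomized 1:1 to CI-CDS intervention or Control".

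Protocol 9.1 still describes a "replication study in up to 30 randomized clinics in a separate health care system", and SAP 2.1 also says that clinics are randomised there. Protocol 9.5.1 specifies a "generalized linear mixed model (LMM) to account for clustering within randomized clinics", with a random clinic intercept as the only random effect, and applies the same approach to the replication site. SAP 2.1 leaves replication randomisation and analysis to a site-specific supplement, which is not among the documents.

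**The concern.** The number of randomised units and the correlation within them set the power of a cluster trial. If about six service areas are randomised, a calculation on 26 clinics treats related clinics as independent and uses a normal reference where only a handful of units were allocated. Part 4 of Section 15.5 calls these clinics highly related, which is its reason for not randomising them separately.

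Two misreadings could follow. A null replication would be read against 80% power that the enrolment floor does not provide. If 9.5.1 is followed literally and areas differ from one another, a positive replication would be tested at more than the nominal 5% error. The 9.7% figure also understates the plan's own worst case.

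**Working it through.** **1. Reproduce Table 2.** Inputs from Protocol 9.2.2: n = 60 per clinic, 1:1 allocation, power 0.80, two-sided alpha 0.05, Neff = N / [1 + (n − 1) × ICC]. For the median cell:

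- N = 26 × 60 = 1,560
- design effect = 1 + 59 × 0.04 = 3.36
- Neff = 1,560 / 3.36 = 464.3

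A two-proportion test with pooled null variance then detects 16.5% against 8%. All 27 cells reproduce, with a largest difference of about 0.05 points. The table is correct for the design it assumes.

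**2. The upper bound.** For 22 clinics, ICC 0.05 and usual care 12%, Neff = 1,320 / 3.95 = 334.2. The detectable rate is 23.7%, as Table 2 shows, so the increase is 23.7 − 12 = 11.7 points. The printed 9.7 equals 21.7 − 12, which is the cell for 26 clinics and ICC 0.04. In the scenario the text names, a 9.7-point increase has 66% power.

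**3. The floor by the Protocol's own method.** Twenty clinics lie below Table 2's smallest row of 22. Neff = 1,200 / 3.36 = 357.1. The detectable rate is 17.9%, and power at 16.5% is 69%.

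**4. Service area as the unit.** The documents give no service-area ICC, so 0, 0.01, 0.02 and 0.04 are assumed. Total same-clinic ICC is held at 0.04, usual care at 8%, and areas are taken as equal in size. With m patients per area:

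- design effect = 1 + 59 × 0.04 + (m − 60) × ICC_area
- λ = (0.165 − 0.08) / √{[0.08 × 0.92 + 0.165 × 0.835] / (Neff / 2)}
- power from a non-central t on (areas − 2) df; the normal figure is Φ(λ − 1.96)

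At the floor m = 1,200 / 6 = 200. With ICC_area 0.01 the design effect is 3.36 + 140 × 0.01 = 4.76, Neff = 252.1, λ = 2.08 and the critical t on 4 df is 2.776, so power is 36%.

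| Areas / clinics | m | ICC_area | Design effect | λ | Power, t | Power, normal |
|---|---|---|---|---|---|---|
| 6 / 20 | 200 | 0 | 3.36 | 2.47 | 47% | 70% |
| | | 0.01 | 4.76 | 2.08 | 36% | 55% |
| | | 0.02 | 6.16 | 1.82 | 29% | 45% |
| | | 0.04 | 8.96 | 1.51 | 22% | 33% |
| 12 / 26 | 130 | 0 | 3.36 | 2.82 | 72% | 80% |
| | | 0.01 | 4.06 | 2.56 | 64% | 73% |
| | | 0.02 | 4.76 | 2.37 | 57% | 66% |
| | | 0.04 | 6.16 | 2.08 | 47% | 55% |
| 16 / 30 | 112.5 | 0 | 3.36 | 3.03 | 80% | 86% |
| | | 0.01 | 3.885 | 2.81 | 74% | 80% |
| | | 0.02 | 4.41 | 2.64 | 69% | 75% |
| | | 0.04 | 5.46 | 2.37 | 60% | 66% |

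The 70% in the first row uses unpooled variance; the Protocol's pooled form gives the 69% of step 3. Detectable rates at the floor, by t, are 21.9%, 25.1%, 28.0% and 32.9%. The 12/26 and 16/30 layouts are illustrations and do not appear in the documents.

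**5. Type I error if the area level is left out.** In 20,000 simulated trials per setting (beta-binomial, 8% in both arms), a t test on clinic means stood in for the clinic-intercept model.

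| Areas / clinics | ICC_area 0.01 | ICC_area 0.02 |
|---|---|---|
| 6 / 20 | 10% | 16% |
| 12 / 26 | 8% | 11% |
| 16 / 30 | 7% | 9% |

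A t test on service-area means stayed at 4.4% to 5.1%. Its simulated power at the floor was 47%, 36%, 30% and 22%, in line with step 4.

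**The case against.** The best defence is that the SAP already sends replication randomisation and analysis to a supplement. The SAP is dated 7/25/2025, after Protocol version 5 of May 08, 2025, so the final model may well include the service area. That stands as far as it goes: the type I error figures apply only if 9.5.1 is followed as written, and they use a stand-in test. It does not repair 9.1, 9.2.2 or 9.5.1, which are current text, nor SAP 2.1, which itself still says clinics are randomised.

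The size of the power loss is also open to challenge. Three areas per arm is a minimum, every service-area ICC here is assumed, and possible stratification by area size is not modelled. At zero area ICC the loss contains no area clustering. Going from 26 to 20 clinics takes power from 80% to 69%, a clinic-level t on 18 df would give 65%, and the rest of the fall to 47% comes from using 4 df. All of that is fair. But the 4 df follow from allocating six units, because the analysis cannot take the area ICC to be zero. With 16 areas and 30 clinics the normal approximation still gives 80% at an area ICC of 0.01.

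Finally, 9.7% is a slip beside a correct table, and 9.5.1 rests effectiveness on the primary site with no pooled analysis. Both points limit the consequence; neither removes the error.

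**Conclusion.** The concern holds and should be fixed. Two parts need no assumption: 9.7% contradicts Table 2 and should read 11.7%, and the replication power describes a unit of randomisation that OCHIN is not using.

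At the enrolment floor the stated 80% is missed whatever the service-area ICC: 69% by the Protocol's own clinic-level method, and 47% down to 22% by an area-level t test over assumed ICCs of 0 to 0.04. Above the floor the answer depends on the number of areas and an ICC that the plan does not state; 16 areas with 30 clinics reaches 80% by t only at zero area ICC. The inflated type I error is conditional on a clinic-only model and an area ICC above zero. The effect is confined to the replication.

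**What to change.** - In Protocol 9.2.2, restate replication power with the actual number of service areas and clinics, the clinic ICC, a stated range of service-area ICC, and a t reference on (areas − 2) df. If power falls below 80%, describe the replication as an estimate with a 95% confidence interval.
- If Table 2 is kept, change 9.7% to 11.7% and label the table as clinic-level.
- Reconcile Protocol 9.1, Protocol 9.5.1 and SAP 2.1 with Section 15.5, so that all say service areas are randomised at OCHIN.
- In 9.5.1 or the supplement, make the service area the top-level cluster: a random service-area effect with small-sample df, or a t test on service-area summaries. Use a permutation test only with enough areas. Unstratified, three against three has 20 allocations and a smallest two-sided p of 2/20 = 0.10; four against four has 70 and can reach 2/70 = 0.029.

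The cost is Protocol and SAP wording, one recalculation and a less favourable stated figure. No extra patients are needed and nothing changes at the primary site.
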